4.2.8 Immunogenicity analysis

Immunogenicity results of all patients will be listed. The number and percentage of patients who develop detectable ADA to MEDI4736 within each ADA response category listed in [section 3.4.2](#) will be summarised based on the ADA analysis set. The immunogenicity titre and neutralising ADA data will be listed for samples confirmed positive for the presence of anti-MEDI4736 antibodies. Details for the presentation and derivation of ADA data is provided in [section 3.4.2](#).

The effect of immunogenicity on PK, efficacy and safety will be evaluated if data allow.

4.2.9 Biomarkers analysis

The relationship between PD-L1 and clinical outcomes PFS, OS, ORR, DoR and PFS2 will be presented; plans for this analysis are detailed in the clinical outcomes [sections 4.2.1](#) (PFS), [4.2.2.1](#) (OS), [4.2.2.3](#) (ORR), [4.2.2.4](#) (DoR) and [4.2.2.7](#) (PFS2).

4.2.10 PK/PD relationships

If the data are suitable, the relationship between durvalumab PK exposure and efficacy/safety parameters may be investigated graphically or using appropriate data modelling approach, which will be presented in a separate exposure-response report.

4.2.11 Demographic and baseline characteristics data

Unless otherwise specified, the following will be summarised for all patients in the mITT set by treatment group, and repeated for ITT set:

- Patient disposition (All patients only)
- Important protocol deviations
- Inclusion in analysis populations
- Demographics (age, age group [< 50 , $\geq 50 - < 65$, $\geq 65 - < 75$ years and additionally ≥ 75 years], sex, race and ethnicity). Age will be derived from the date of informed consent
- Patient characteristics at baseline (height, weight, weight group [< 70 , 70 to 90 and > 90 kg], body mass index (BMI) and BMI group)
- Patient recruitment by region, country and centre
- Prior radiotherapy and chemotherapy

- Time from last dose of radiation to randomisation, and time from last dose of radiation to randomisation group (< 14 days vs. ≥ 14 days)
- Disease characteristics at baseline (WHO performance status, primary tumour location, histology type, AJCC staging and overall disease classification, best response to previous therapy, EGFR status, ALK status and combined EGFR/ALK status)
- Extent of disease at study entry
- TNM classification at baseline
- Medical history (past and current)
- Relevant surgical history (as appropriate)
- Disallowed concomitant medications
- Allowed concomitant medications
- Post-discontinuation cancer therapy
- Nicotine use, categorised (never, current, former)
- Stratification factors (level of PD-L1 expression, prior therapy) as per IVRS and eCRF data. In addition, cross tabulation will be provided for prior therapy per IVRS with eCRF data.

Information on EGRF/ALK status will be based on eCRF data. The combined EGRF/ALK status (i.e. “EGRF mutation or ALK rearrangement”) will be classified as ‘positive’ if positive for either EGFR mutation or ALK rearrangement, ‘negative’ if both are negative, ‘unknown’/’missing’ if both are unknown/missing. In case of multiple sources, i.e. records from both local and central laboratories, data from the central laboratory will be used. These descriptions of EGRF and/or ALK status are only applicable on the ITT set.

The demographic characteristics at baseline and ECOG performance along with past medical history and ongoing conditions will be summarised additionally in patients with confirmed or suspected COVID-19 infection.

The patient disposition table will be repeated on the mITT population without counts of patients enrolled and screen failure description.

Demographic and baseline characteristics will also be listed.

4.2.12 Treatment exposure and intensity

The following summaries related to study treatment will be produced for the safety analysis set by treatment group:

- Total exposure
- Actual exposure (durvalumab or matching placebo only)

- Reasons for dose delays/interruptions. Dose interruptions will be based on investigator initiated dosing decisions
- Number of infusions received
- Relative dose intensity (RDI) (durvalumab or matching placebo only)
- Cumulative exposure over time

For patients on study treatment at the time of the IA, the DCO date will be used to calculate exposure.

4.2.13 Impact of COVID-19

Depending on the extent of any impact, summaries of data relating to impact of COVID-19 on study conduct may be generated, including:

- Disposition (discontinued IP due to COVID-19 and withdrew study due to COVID-19)
- Deviations (overall deviations plus if due to COVID-19 and not due to COVID-19)
- Summary of COVID-19 disruption (visit impacted, drug impacted)
- Summary of confirmed/suspected COVID-19 infections for all patients and for patients who died.
- PFS sensitivity analysis (see more details in [section 4.2.1](#))
- OS sensitivity analysis (see more details in [section 4.2.2.1](#))
- COVID-19 related death (see more details in [section 4.2.5.1](#))
- a repeat of the main AE summary table, if more than 20 patients

These confirmed/suspected AEs will also be listed.

4.2.14 China Cohort Analyses

Per China National Medical Products Administration's (NMPA) guidance, in addition to the evaluation of the global cohort data for primary, secondary and safety objectives, evaluation of consistency in efficacy and safety between the China subgroup and the overall global cohort is required to facilitate the benefit-risk assessment for China patients.

The efficacy and safety data for the China cohort are summarised and analysed using the same methodology as described above for the overall global population.

All statistical analyses in the China cohort will be considered as exploratory, and therefore no alpha is assigned to the efficacy assessment for this cohort.

5 INTERIM ANALYSES

5.1 Analysis methods

Interim safety monitoring will be conducted by an IDMC. The recommendations from the IDMC will not reveal the results of the analysis but will take the form of 'Continue/Modify/Stop'. Interim analyses will be performed for efficacy as described below. The OS interim analysis will be conducted by study team and will not be reviewed by IDMC as the study will be unblinded at PFS final (primary) analysis.

5.1.1 OS interim analyses

Up to two OS IAs will be performed for superiority, in the mITT set. The DCO for the first IA of OS will occur at the same time as final (primary) PFS analysis (estimated approximately [REDACTED] OS events in the mITT set at the time of the analysis). The second IA of OS will be conducted at approximately [REDACTED] months after the first OS interim analysis (approximately [REDACTED] OS events in the mITT with [REDACTED] maturity), which may be removed as specified in section 1.3.

The alpha level allocated to OS will depend on the results of the PFS analysis (see [section 4.1.2](#)). It will be controlled at the interims and final analysis by using the Lan DeMets ([Lan and DeMets 1983](#)) spending function that approximates an O'Brien Fleming approach, where the significance level applied at the IA depends upon the proportion of information available.

The significance level for the OS analyses will be calculated using the statistical software package EAST by specifying the information fraction for each analysis. The information fraction is calculated as the number of OS events at the analysis time-point divided by the total number of events at the final analysis time-point. For example, if the alpha level available for OS is 5%, and if [REDACTED] or [REDACTED] of OS events required at the time of the final OS analysis are available at the time of the interim analysis (i.e., [REDACTED] or [REDACTED] OS events have occurred), the 2-sided significance level to be applied for the OS IA would be [REDACTED] and [REDACTED] respectively, and the 2-sided significance level to be applied for the final OS analysis would be [REDACTED].

5.1.2 Independent Data Monitoring Committee

An IDMC composed of independent experts will be convened to confirm the safety and tolerability of the proposed dose and schedule of durvalumab. The first safety review will take place approximately 6 months after FSI and then periodically in accordance with the IDMC charter to continue safety monitoring until final PFS analysis. Additional reviews of the safety data may be requested by the IDMC at additional points during the study.

Safety reviews will be carried out by the IDMC in an unblinded manner. After review of the unblinded data, the IDMC will make a recommendation on whether the study should continue recruitment as planned or hold recruitment.

Full details of the IDMC procedures, processes can be found in the IDMC Charter.

6 CHANGES OF ANALYSIS FROM PROTOCOL

Time to deterioration in patient-reported symptoms, functioning and global health status/QoL was added as secondary endpoint considering relevant analysis for this endpoint was described in the CSP.

For the definition/derivation of TTDM, distant metastasis is defined as any new lesion that is outside of the radiation field according to RECIST 1.1 only. New lesion proven by biopsy will not be used for distant metastasis identification.

8 APPENDIX

APPENDIX A. 2 MISSED VISITS

ePRO Assessments

As per Section 3.2.3.1, confirmation of deterioration/worsening will first be determined, then the censoring rules will be applied. For ePRO assessments, we will apply a ‘look-forward’ approach to the 2 missed visit rule.

For example:

Baseline	V1	V2	V3	V4	V5	V6	V7	V8	Observed confirmed deterioration visit*	Time to Deterioration derivation
	NC	DT	DT	NC	MV	NC	IMP	NC	Event at V2	Event at V2
	MV	MV	NC	DT	MV	DT	DT	NC	Event at V4	No event, censor at baseline
	MV	DT	NC	MV	MV	DT	DT	NC	Event at V6	No event, censor at V3
	NC	DT	NC	MV	IMP	DT	NC	DT	Event not confirmed, but if last DT then confirmed	Event at V8

	NC	DT	NC	MV	IMP	DT	MV	DT	Event at V6	Event at V6
	NC	IMP	NC	IMP	MV	MV	IMP	DT	Event at V8, last DT	No event, censor at V4
	MV	MV	NC	MV	MV	DT	DT	NC	Event at V6	No event, censor at baseline
	NC	DT	MV	MV	DT	NC	IMP	DT	Event at V2	Event at V2

DT Deterioration; IMP Improvement; MV Missed visit; NC No change (/stable).

*Missed visits are allowed in between assessments confirming deterioration/worsening, and confirmation of deterioration/worsening requires at least 14 days between assessments.

Length of 2 missed visit window for EORTC QLQ-C30 and QLQ-LC13

The scheduled visit assessments and visit windows for the QLQ-C30 and QLQ-LC13 are every 4 weeks (± 1 week) for the first 8 weeks from randomization, and then every 8 weeks (± 1 week) up to 48 weeks relative to date of randomization, and then every 12 weeks (± 1 week) until confirmed PD by RECIST 1.1 per Investigator assessment, and then every 12 weeks (± 1 week) thereafter until PFS2.

Missing baseline or within 2 visits of baseline:

- A patient without baseline will be censored at day 1 unless they die \leq day 63.
- Any assessment \leq day 63 is within 2 visits (2×4 weeks + 1 week) of baseline and therefore cannot be censored for missing visits.

Schedule: q4w ± 1 week:

For any assessment $>$ day 1 then visit schedule is q4w ± 1 week and thus the maximum time between 2 consecutive assessments is $7+28+28+7=70$ days.

Schedule: q8w ± 1 week:

- For any assessments where the visit schedule changes from q4w ± 1 week to q8w ± 1 week, the maximum time between 2 consecutive assessments is $7+28+56+7 = 98$ days.
- For any assessments where the visit schedule is q8w ± 1 week, the maximum time between two consecutive assessments is $7+56+56+7 = 126$ days.

Schedule: q12w \pm 1 week:

- For any assessments where the visit schedule changes from q8w \pm 1 week to q12w \pm 1 week, the maximum time between 2 consecutive assessments is $7+56+84+7 = 154$ days.
- For any assessments where the visit schedule is q12w \pm 1 week, the maximum time between two consecutive assessments is $7+84+84+7 = 182$ days.

SIGNATURE PAGE

This is a representation of an electronic record that was signed electronically and this page is the manifestation of the electronic signature

Document Name: d933yc00001-sap-ed-3		
Document Title:	Statistical Analysis Plan Edition 3	
Document ID:	CCI [REDACTED]	
Version Label:	3.0 CURRENT LATEST APPROVED	
Server Date (dd-MMM-yyyy HH:mm 'UTC'Z)	Signed by	Meaning of Signature
20-Mar-2024 14:09 UTC	PPD [REDACTED]	Content Approval

CCI [REDACTED]

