Informed consent: tumour sample collection ^c (part I screening ICF)	X							5.1
Informed consent: study procedures ^c (part II screening ICF)		Х						5.1
Study procedures						•		·
Physical exam (full)		Х						8.2.2
Targeted physical exam (based on symptoms)			Х	Х	X	X	Х	8.2.2
Vital signs		Х	Х	Х	Х	Х	Х	8.2.3
Weight		Х	Х	Х	Х	X	Х	8.2.3
ECG ^d		Х			As clin	nically indicated		8.2.4
Concomitant medications		<					>	6.4
Demography	X							5.1
Tobacco use		Х						5.1
Eligibility criteria	Х	Х	Х					5.1, 5.2
Randomisation			Х					6.2
Laboratory assessments								
Clinical chemistry ^e		Х	X ^f	Х	Х	Х	Х	Table 7
Haematology ^e		Х	\mathbf{X}^{f}	Х	Х	Х	Х	Table 8

	Screening Visit Part I	Screening Visit Part II	C1	C2	C3	C4	C5 to PD	
Week	-12 to -1	-4 to -1	0	q4w ±3	days unless dos	ing needs to be l	held for toxicity reasons	For details,
Day	-84 to -1	-28 to -1	1 ^b	q28d ±3	3 days unless dos	sing needs to be	held for toxicity reasons	see Section
Coagulation		Х			As clir	nically indicated		Table 9
TSH (reflex free T3 or free T4 ^g)		Х	X ^h	Х	Х	Х	Х	Table 7
Urinalysis		Х			As clir	nically indicated		Table 10
Hepatitis B and C and HIV		Х						8.2.6
Pregnancy test ^{ij}		Х	Х	Х	Х	Х	Х	8.2.1
Pharmacokinetics								
CCI								8.5
Monitoring								
WHO/ECOG performance status		Х	х	X	x	х	Х	8.2.5
AE/SAE assessment ¹		<					>	8.3
IP administration								
Durvalumab (monotherapy)/placebo ^m			Х	Х	X	Х	Х	6.1.1.1, 6.1.2.1
Other assessments and assays					•			
CCI						j		8.5
CCI								8.8.2
CCI								8.8.2

	Screening Visit Part I	Screening Visit Part II	C1	C2	C3	C4	C5 to PD	
Week	-12 to -1	-4 to -1	0	q4w ±3	$q4w \pm 3$ days unless dosing needs to be held for toxicity reasons			
Day	-84 to -1	-28 to -1	1 ^b	q28d ±3	For details, see Section			
EORTC QLQ-C30, QLQ-LC13, and EQ-5D-5L ⁿ			х	q4w (±1 week) for the first 8 weeks (relative to the date of Cycle 1 Day 1 visit date i.e. date of randomization/first dose), q8w(±1 week) thereafter until the 48th week (relative to the date of Cycle 1 Day 1 visit date i.e. date of randomization/first dose), and then q12w(±1 week) thereafter until confirmed PD by RECIST 1.1 by investigational site review				8.1.4
Health resource use (HOSPAD)			Х	Х		Х	Х	8.9
CCI								8.8.1
CCI								6.2.1
Efficacy evaluations		-						

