For each of the symptoms scales/items in the EORTC QLQ-C30 and QLQ-LC13, time to symptom deterioration/worsening will be defined as the time from randomisation until the date of the first clinically meaningful symptom deterioration/worsening (an increase in the score from baseline of ≥ 10) that is confirmed at the next available subsequent assessment at least 14 days apart, or death (by any cause) in the absence of a clinically meaningful symptom deterioration/worsening, regardless of whether the patient withdraws from IP or receives another anti-cancer therapy prior to symptom deterioration/worsening. Missed visits are allowed in between assessments confirming deterioration/worsening. This is considered a conservative approach whereby a deterioration/worsening is considered a 'negative' outcome and therefore should be assigned as such, regardless of missed visits. Death will be included as an event only if the death occurs within 2 visits of the last PRO assessment where the symptom change could be evaluated. Patients with a single deterioration/worsening and no further assessments will be treated as deteriorated in the analysis.

Patients whose symptoms (as measured by EORTC QLQ-C30 and QLQ-LC13) have not shown a clinically meaningful deterioration/worsening and who are alive at the time of the analysis will be censored at the time of their last PRO assessment where the symptom could be evaluated. Also, if symptoms deteriorate after 2 or more missed PRO assessment visits or the patient dies after 2 or more missed PRO assessment visits, the patient will be censored at the time of the last PRO assessment where the symptom could be evaluated, prior to the 2 missed assessment visits. The 2 missed visit rule for ePRO will take a 'look-forward' approach i.e. if there are 2 consecutive missed visits at any time prior to the confirmed deterioration event, the event will be censored at the last available assessment prior to the 2 missed visits. Confirmation of deterioration will be first determined, then the censoring rules will be applied.

See Appendix A for further details on the derivation of the confirmation of deterioration 2 missed visit rule for ePRO and length of 2 missed visit window.

If the patient has no evaluable visits or does not have baseline data, they will be censored at day 1 unless they die within 2 visits of baseline (8 weeks plus 3 days allowing for a late assessment within the visit window).

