The population for the analysis of time to symptom deterioration will include patients who have baseline scores of ≤ 90 .

Time to HRQoL/function deterioration/worsening (QLQ-C30)

For HRQoL and function (as measured by EORTC QLQ-C30), time to deterioration/worsening will be defined as the time from the date of randomisation until the date of the first clinically meaningful deterioration/worsening (a decrease in the function scales or the global health status/QoL score from baseline of ≥ 10) that is confirmed at the next available subsequent assessment at least 14 days apart, or death (by any cause) in the absence of a clinically meaningful deterioration/worsening, regardless of whether the patient withdraws from IP or receives another anti-cancer therapy prior to HRQoL/function deterioration/worsening. Missed visits are allowed in between assessments confirming deterioration. This is considered a conservative approach whereby a deterioration is considered a 'negative' outcome and therefore should be assigned as such, regardless of missed visits. Death will be included as an event only if the death occurs within 2 visits of the last PRO assessment where the HRQoL/function change could be evaluated. Patients with a single deterioration/worsening and no further assessments will be treated as deteriorated in the analysis.

Patients whose HRQoL or function have not shown a clinically meaningful deterioration/worsening and who are alive at the time of the analysis will be censored at the time of their last PRO assessment where the HRQoL/function could be evaluated, prior to the 2 missed visits. Also, if HRQoL or function deteriorates after 2 or more missed PRO assessment visits or the patient dies after 2 or more missed PRO assessment visits, the patient will be censored at the time of the last PRO assessment where HRQoL/function could be evaluated. The 2 missed visit rule for ePRO will take a 'look-forward' approach i.e. if there are 2 consecutive missed visits at any time prior to the confirmed deterioration event, the event will be censored at the last available assessment prior to the 2 missed visits. Confirmation of deterioration will first be determined, then the censoring rules will be applied. If the patient has no visits or does not have baseline data, they will be censored at day 1 unless they die within 2 visits of baseline (8 weeks plus 3 days allowing for a late assessment within the visit window).

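### The 70-day PRO missed-visit limit in SAP Appendix A fits no post-baseline visit and conflicts with the 98-day limit at week 4; the early-death cut-offs also disagree (59 versus 63 days)

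*SAP*

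**What the plan says.** **Schedule.** Appendix A has PRO forms every 4 weeks "for the first 8 weeks from randomization, and then every 8 weeks" to week 48, then every 12 weeks, each with a window of 1 week either side. The protocol's Schedule of Activities agrees: 4-weekly to week 8, then 8-weekly "thereafter until the 48th week (relative to the date of Cycle 1 Day 1 visit date i.e. date of randomization/first dose", then 12-weekly, with the same window.

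**Censoring rule.** SAP Section 3.2.3.1 censors "if symptoms deteriorate after 2 or more missed PRO assessment visits or the patient dies after 2 or more missed PRO assessment visits". It adds a look-forward condition: two missed visits in a row anywhere before the confirmed event send the participant back to the last assessment before the gap. A death counts only if it falls within two visits of the last evaluable PRO assessment.

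**Limits in days (Appendix A).** For any assessment after day 1 the schedule is taken as 4-weekly, "and thus the maximum time between 2 consecutive assessments is" 70 days. The next line begins "For any assessments where the visit schedule changes from q4w" and gives 98 days for the change to 8-weekly. Further lines give 126, 154 and 182 days. None is tied to a study-day range.

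**Early deaths.** Appendix A says "A patient without baseline will be censored at day 1 unless they die" by day 63. Section 3.2.3.1 uses "8 weeks plus 3 days allowing for a late assessment within the visit window" for both the symptom and the HRQoL/function endpoints.

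**The concern.** The schedule contains only two 4-week intervals: baseline to week 4, and week 4 to week 8. A limit built from two 4-week intervals plus a window at each end therefore describes a situation that cannot arise after baseline. Yet the 70-day line is worded to cover every post-baseline assessment, and a week-4 assessment also meets the description of the 98-day line.

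The look-forward condition makes this matter. Once a gap has been classed as two missed visits, any later confirmed deterioration is discarded, however long after the gap it occurs. A single missed week-8 form could thus remove a real event and replace it with censoring at week 4. A death 71 to 98 days after a last assessment at week 4 could be dropped in the same way. Time to deterioration is a listed secondary endpoint (SAP Sections 1.1.2 and 6), analysed for each scale in the mITT and repeated in the ITT.

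**Working it through.** **Step 1: the SAP's own sums.** 7+28+28+7 = 70; 7+28+56+7 = 98; 7+56+56+7 = 126; 7+56+84+7 = 154; 7+84+84+7 = 182; 2×28+7 = 63; 8×7+3 = 59. All add up. The question is which assessment each one applies to.

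**Step 2: gaps the schedule allows.** Visits are at weeks 0, 4, 8, 16, 24, 32, 40, 48, 60, 72 and so on. Let a and b be the next two scheduled intervals after the last completed form. If exactly one visit is missed, the gap to the next completed form runs from a+b−14 to a+b+14 days. From baseline, which has no window of its own, it runs from a+b−7 to a+b+7. The longest such gap is the correct limit, since anything longer implies a second missed visit.

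| Last form completed | a + b (days) | Shortest / nominal / longest gap, one visit missed | Appendix A limit |
|---|---|---|---|
| Baseline | 28+28 | 49 / 56 / 63 | 63 |
| Week 4 | 28+56 | 70 / 84 / 98 | 70 and 98 |
| Weeks 8 to 32 | 56+56 | 98 / 112 / 126 | 126 |
| Week 40 | 56+84 | 126 / 140 / 154 | 154 |
| Week 48 onward | 84+84 | 154 / 168 / 182 | 182 |

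No row has 70 as its longest gap. The 126-day line and the 70-day line also overlap from week 8 onward, because the 70-day wording covers all assessments after day 1.

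**Step 3: effect at week 4.** With randomisation as day 1, the week-4 form falls on days 22 to 36 and the week-16 form on days 106 to 120. That gives 15×15 = 225 in-window combinations when only week 8 is missed. Of these, 224 exceed 70 days; the exception is day 36 to day 106, exactly 70. None exceeds 98. When weeks 8 and 16 are both missed and week 24 is attended, the gap is 126 to 154 days, so a 98-day limit still catches every true case.

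**Step 4: the other way to share out the lines.** Suppose 70 days is used for week 4 and the 98-day line is assigned to week 8. Missing only week 16 then gives a gap of 98 to 126 days, and 224 of 225 combinations exceed 98. Both limits would be too short.

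**Step 5: early deaths.** The cut-offs are 59 and 63 days, 4 days apart. Two 4-week visits plus the scheduled 1-week window give 56+7 = 63 elapsed days. The 59-day figure needs a 3-day window, which is not the PRO window. If randomisation is study day 1, a week-8 form 7 days late falls on study day 57+7 = 64, so the appendix's day 63 also needs to say whether it is a study day or elapsed days.

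**The case against.** The best defence is that the SAP already contains the right answer. The 98-day line addresses exactly the change from 4-weekly to 8-weekly visits, and a specific rule normally overrides a general one. In addition, the rule in Section 3.2.3.1 counts visits, and so do the worked examples in Appendix A: the fourth and fifth rows have only isolated missed visits and keep their events, at visits 8 and 6. A program built on visit counts would not censor someone who missed only week 8.

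This stands as a reason to expect that a careful programmer would reach 98 days. It does not clear the text. On that reading the 70-day line applies to no visit at all, although it is worded to cover all of them, and without day ranges nothing in the appendix settles the choice. The examples show that a 70-day reading contradicts the SAP's own rule, which is a further reason to remove the line. PFS Table 6 shows the better form: it ties each limit to a study-day range and gives the mixed interval to the last visit before the spacing changes.

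On early deaths, both time-to-deterioration populations require a qualifying baseline score, and Protocol Section 9.4.3.3 excludes participants without baseline data. That narrows the conflict further, mainly to participants who have a baseline form but no later evaluable one. The SAP does not say where the 3 days come from. The dosing-visit window in the Schedule of Activities is 3 days, but a link is only a guess.

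**Conclusion.** One limit in Appendix A is mis-scoped, and one early-death cut-off is stated in two ways. Both need correcting in the text.

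The harm from the 70-day line is conditional. It requires that the program uses 70 days; that the participant completes week 4, misses only week 8 and returns at week 16; and that the first confirmed deterioration comes after that gap. For deaths, it requires a last form at week 4 and death 71 to 98 days later. The 59/63-day conflict touches only deaths in a span of about 4 days, among participants with no evaluable visits or no baseline.

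Four stronger readings are tempting but not supported:

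- **That the PRO limits are wrong in general.** The sums are correct, and 63, 98, 126, 154 and 182 days are the right limits for the assessments in the table above.
- **That events will be lost.** This depends on which line is programmed, which the documents do not show.
- **That the number lost can be estimated.** Assuming that 5 to 15% of about 375 mITT participants miss week 8 gives 0.05×375 ≈ 19 to 0.15×375 ≈ 56. The percentages are an assumption, and the result is a ceiling on participants exposed, not a count of events. It also does not follow that every scale is affected: a scale loses an event only if its first confirmed event follows the gap.
- **That trial conclusions are at risk.** Time to deterioration is outside the alpha-controlled sequence, which covers PFS and OS only. PFS has its own table, and the PRO mixed-model analysis of change from baseline does not use this rule.

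**What to change.** In Appendix A, delete the 70-day line and replace the bullets with a table in the style of SAP Table 6, keyed to the last assessment:

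- Baseline: 63 elapsed days
- Week 4: 98 days
- Weeks 8 to 32: 126 days
- Week 40: 154 days
- Week 48 onward: 182 days

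If the ranges start at the early edge of each visit window, as Table 6 does, the study-day boundaries are 29−7 = 22, 57−7 = 50, 281−7 = 274 and 337−7 = 330.

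Use one early-death cut-off, 8 weeks plus 1 week, in both places in Section 3.2.3.1 and in Appendix A. State that it means 63 elapsed days from randomisation, which is study day 64 if randomisation is day 1.

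The cost is a short SAP text change and a check of one derivation in the PRO programs. No data collection changes.
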